**Safety Assessments:**

Serum troponin and ECGs will be obtained as part of the Screening visit, before and/or after dosing on selected days. Refer to Schedule of Events for timing.

Safety assessments include medical history, physical examinations, SET as determined by TTE, 12-lead ECGs, continuous ECG monitoring by (a) telemetry, (b) Holter monitor recording or (c) equivalent technology, vital signs, observed and patient-reported AEs, serum troponin concentrations, and safety laboratory tests. Any abnormal findings judged by the investigator to be clinically relevant will be recorded as AEs.

Suspected ischemic events, new or worsening episodes of ventricular arrhythmias and troponin elevations will be sent for review by a Central Safety Adjudication Committee (see [Section 4.5](#)).

Statistical Analyses:**General Considerations:**

Clinical data will be analyzed separately for the SAD and MAD parts of the study. In Part 1, the placebo dosing periods will be pooled across cohorts to form a placebo group. Placebo subjects from all MAD Cohorts will be pooled to form one combined placebo group for analyses. No formal statistical hypothesis testing will be performed. Descriptive summary statistics for continuous variables will include the number of participants, mean, standard deviation (SD), median, 1st and 3rd quartiles, minimum, and maximum. Categorical variables will be summarized using counts and percentages. The 95% confidence intervals may be presented as well.

Safety Analyses:

SET, as determined by TTE, will be assessed using summary statistics. Observations and change from Baseline will be summarized by treatment at each timepoint and the

maximum change from Baseline will be determined for each patient. [REDACTED]

[REDACTED]

[REDACTED]

The number of patients with abnormal and/or rising troponin levels (taking into account potential troponin elevation at Baseline) will be determined.

Continuous ECG recordings by telemetry or Holter monitor (or equivalent) will be used to assess the nature, frequency, and severity of any ventricular arrhythmias or other significant cardiac rhythm abnormalities.

AEs, ECGs, vital signs, and laboratory values will be analyzed using descriptive statistics.

Pharmacokinetic Analyses:

The PK population will include all patients who receive MYK-491, have detectable plasma concentration data, and have no major or critical protocol deviations related to IMP (eg, incomplete ingestion of the drug, vomiting up to 8 hours after drug administration). In addition, a single plasma sample near the predicted time of maximum observed plasma concentration (T_{max}) of MYK-491 will be evaluated to confirm lack of circulating MYK-491 for the dosing period(s) when the patients received placebo.

Plasma concentration [REDACTED] data for MYK-491 will be summarized using descriptive statistics, including mean or geometric mean, as appropriate, SD, median, minimum and maximum values, and coefficient of variation (CV%). Other PK parameters include (but are not limited to) maximum observed plasma drug concentration (C_{max}), T_{max} , area under the plasma concentration-time curve over the dosing interval (AUC_{0-t}), AUC_{0-12} , AUC_{0-24} , AUC_{0-inf} after the single dose on Day 1 in Part 1 or Days 3 and 9 in Part 2 (in appropriate patients), trough concentration (C_{trough}), apparent first-order terminal elimination rate constant (λ_z) (on Day 1 in Part 1 and Day 9 in Part 2 only), and mean residence time (MRT). PK parameters at steady-state will be compared to those observed after the first dose in this study, and the accumulation ratios determined (with the appropriate confidence intervals) based on C_{max} and AUC_{0-t} after a single dose and at steady-state as well as λ_z . Additionally, the apparent terminal-phase elimination half-life ($t_{1/2z}$) will be calculated after each dosing day in Part 1 and on Day 7 in appropriate patients. [REDACTED]

[REDACTED]

Pharmacodynamic Analyses:

The PD Analysis population will include patients who have any interpretable TTE data. TTE data for LVSV (derived from LVOT-VTI), LVEF, LVFS, and SET will be analyzed using descriptive statistics. Observations by timepoint and change from Baseline (predose in that dosing period) for each timepoint will be summarized by treatment arms. Change from Baseline will be analyzed with attention to relationship to time postdose, dose level, and comparison with placebo. For SAD Cohorts, placebo-adjusted change from Baseline will be calculated for each subject at each postbaseline timepoint and then summarized at each dose level. In addition, for SAD and MAD Cohorts, least square means of placebo-adjusted change from Baseline for the key PD parameters (LVSV [derived from

LVOT-VTI], LVEF, LVFS, SET) at each postbaseline time point at each dose level may be estimated using mixed model.

Pharmacokinetic/Pharmacodynamic Analyses:

Correlations of LVSV (derived from LVOT-VTI), LVEF, LVFS, SET, and/or vital signs with MYK-491 dose and/or plasma concentration may be assessed.

Sample Size Considerations:

No formal statistical hypothesis testing will be performed. In Part 1, enrollment of 4-8 patients per cohort is planned and in Part 2, 8 patients per cohort with the potential to expand to 24 patients, with up to an additional 2 replacements per cohort, in order to meet study objectives. Based on the study design, the sample size is considered appropriate to explore tolerability and safety parameters, PK profile, and PD effects of MYK-491.

Compliance Statement:

This study will be conducted in accordance with the International Council for Harmonisation (ICH) Good Clinical Practice (GCP) guidelines; US Title 21 Code of Federal Regulations (CFR) Parts 11, 50, 54, 56, and 312; European Union (EU) GCP and Good Manufacturing Practices (GMP); and the principles enunciated in the Declaration of Helsinki and all human clinical research regulations where the study is to be conducted.

TABLE OF CONTENTS

CLINICAL TRIAL PROTOCOL	1
SYNOPSIS.....	2
TABLE OF CONTENTS.....	14
LIST OF TABLES.....	18
LIST OF FIGURES	18
LIST OF ABBREVIATIONS AND DEFINITIONS OF TERMS.....	19
1 INTRODUCTION	22
1.1 Background	23
1.1.1 In Vitro Studies	23
1.1.3 Drug Metabolism	24
1.1.5 MYK-491	25
1.2 Clinical Studies	25
1.3 Known and Potential Risks and Benefits.....	26
2 RATIONALE FOR THE STUDY AND FOR DOSE AND DOSING SCHEDULE.....	28
2.1 Rationale for the Study	28
2.2 Rationale for Dose and Dosing Schedule	28
2.2.1 Part 1 (SAD) Cohort 1 Dose Levels	28
2.2.1.1 Low-Dose Level Cohort 1	28
2.2.1.2 Second Dose Level Cohort 1	28
2.2.1.3 Third Dose Level Cohort 1	29
2.2.2 Part 1 (SAD) Cohort 2 Dose Levels	29
2.2.3 Part 2 (MAD) Cohort A Dose	29
2.2.4 Part 2 (MAD) Cohorts B and C Doses.....	30
2.3 Rationale for Exceeding NOAEL	30
3 STUDY OBJECTIVES.....	32
3.1 Primary Objective	32
3.2 Secondary Objectives.....	32
4 OVERALL STUDY DESIGN AND PLAN.....	33
4.1 Study Design.....	33
4.1.1 Part 1 Study Design	33
4.1.2 Part 2 Study Design	34
4.2 Stopping Criteria.....	37
4.2.1 Stopping Criteria for an Individual Participant in Part 1 (SAD)	37

4.2.2	Criteria for Unscheduled SRC Review of the Study in Part 1 (SAD)	38

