This is a two-part study. Part 1 will evaluate single-ascending doses of MYK-491 (SAD Cohorts) and Part 2 will evaluate multiple, ascending doses of MYK-491 (MAD Cohorts). Note: Part 2 (MAD portion) of the study is planned to start before Cohort 2 of Part 1 (SAD Cohort) is complete. If a patient at a site qualifies for enrollment in either Part 1 (SAD) or Part 2 (MAD), Part 2 (MAD) will generally take priority; however, a patient may enroll in both, ie Part 1 (SAD) followed by Part 2 (MAD) or Part 2 (MAD) followed by Part 1 (SAD). In such cases, sites should consult with the monitoring team to discuss details.

Part 1-Single, ascending doses (SAD Cohorts): This is a randomized, crossover, double-blind (DB), placebo-controlled, two-cohort, sequential ascending (oral) single-dose study in ambulatory patients with heart failure. All patients will receive placebo and 2 or 3 active doses of MYK-491. Each patient will undergo sequential, single-dose treatment events separated by no fewer than 5 days and no more than 14 days. Patients in Cohort 1 may also return for a fourth dosing period (open label) after the SRC reviews available data and recommends the dose. Patients enrolled prior to the implementation of Amendment 1 may be offered the opportunity to return for the open-label period. Patients who return for this additional period must sign the amended informed consent form (ICF). Patients in Cohort 2 may participate in 2-4 dosing periods, based on SRC decision. Patients will be randomized to 1 of the different dosing sequences outlined in [Figure 1](#). Multiple patients

can be dosed at the same time or during the same week depending on administrative issues, ie, capacity and scheduling.

For each dosing period, patients will be admitted to the clinical site on Day -1, (the day before dosing). Patients will be assessed for absence of exclusion criteria (eg, new lab abnormalities based on local labs and/or conditions that indicate the patient is clinically unstable). They will receive MYK-491 or placebo in the morning of Day 1 followed by serial PK and PD assessments, as well as serial safety assessments. Patients will be discharged on Day 3 (ie, ~48 hours following Day 1 dosing). An additional outpatient plasma PK sample will be taken on the morning of Day 4 at 72 hours postdose.

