4 OVERALL STUDY DESIGN AND PLAN

4.1 Study Design

This is a two-part study. Part 1 will evaluate single-ascending doses of MYK-491 (SAD Cohorts) and Part 2 will evaluate multiple-ascending doses of MYK-491(MAD Cohorts).

Note: Part 2 (MAD portion) of the study is planned to start before Cohort 2 of Part 1 (SAD Cohort) is complete. If a patient at a site qualifies for enrollment in either Part 1 (SAD) or Part 2 (MAD), Part 2 will generally take priority; however, a patient may enroll in both, ie Part 1 (SAD) followed by Part 2 (MAD) or Part 2 (MAD) followed by Part 1 (SAD). In such cases, sites should consult with the monitoring team to discuss details.

4.1.1 *Part 1 Study Design*

Part 1 is a randomized, crossover, DB, placebo-controlled, two-cohort, sequential ascending (oral) single-dose study in ambulatory patients with heart failure. All patients will receive placebo and 2 or 3 active doses of MYK-491. Each patient will undergo sequential, single-dose treatment events separated by no fewer than 5 days and no more than 14 days. Patients in Cohort 1 may also return for a fourth dosing period (open label) after the SRC reviews available data and recommends the dose. Patients enrolled prior to the implementation of Amendment 1 may be offered the opportunity to return for the open-label period. Patients who return for this additional period must sign the amended informed consent form (ICF). Patients in Cohort 2 may participate in 2 to 4 dosing periods, based on SRC decision. Patients will be randomized to 1 of the different dosing sequences outlined in [Figure 1](#). Multiple patients can be dosed at the same time or during the same week depending on administrative issues, ie, capacity and scheduling.

For each dosing period, patients will be admitted to the clinical site on Day -1. Patients will be assessed for absence of exclusion criteria (eg, new lab abnormalities and/or conditions that indicate the patient is clinically unstable). They will receive MYK-491 or placebo in the morning of Day 1 followed by serial PK and PD assessments, as well as serial safety assessments. Patients will be discharged on Day 3 (ie, ~48 hours following Day 1 dosing). An additional outpatient plasma PK sample will be taken on the morning of Day 4 at 72 hours postdose.

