Before administering a dose, the investigator or the subinvestigator will review all available safety data, including vital signs, safety laboratory values including locally assayed troponin concentrations, TTEs, ECGs, and ECG telemetry. Dosing with DB treatment will take place at the same time each of the dosing days. Background concomitant medications, including diuretic if applicable, should also be administered at same time each of the dosing days. Prior to dosing, any patient with a predose resting HR ≥ 95 bpm will be considered ineligible and not treated. HR is the mean of 3 measurements.

A full PK profile and multiple TTEs and ECGs will be obtained at Baseline and after each dose. Patients will return for a final safety Follow-up visit 7 days (± 1 day) following the last dose.

During the study, the patients should continue to ingest their medications for the treatment of their congestive heart failure and other medical conditions at the same doses and as close to the same times as usual.

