Plasma [REDACTED] concentration data for MYK-491 will be summarized using descriptive statistics, including mean or geometric mean as appropriate, SD, median, minimum, and maximum values and CV%. PK parameters will include (but are not limited to) C_{max} , T_{max} , AUC, apparent first-order terminal elimination rate constant (λ_z), and MRT. In addition, the accumulation ratios will be calculated with C_{max} and AUC_{0-t} (t = dose interval or τ) after dose on Day 9 (at steady-state) and Day 3 (1st dose). Additionally, the apparent terminal-phase elimination half-life ($t_{1/2z}$) will be calculated.

[REDACTED]

[REDACTED]

11.3.6 *Pharmacodynamic Analyses*

TTE data for LVEF, SET, LVFS, LHSV will be analyzed using descriptive statistics. No inferential analysis will be performed. Observations by timepoint and change from Baseline (either absolute or percent relative change) at each timepoint will be summarized by treatment period (Part 1) and treatment group (Part 2). Change from Baseline will be analyzed with attention to the relationship to time postdose, dose level, and comparison with placebo. For SAD Cohorts, placebo-adjusted change from Baseline will be calculated for each subject at each postbaseline timepoint and then summarized at each dose level. In addition, for SAD and MAD Cohorts, least square means of placebo-adjusted change from Baseline for the key PD parameters (LVEF, LVFS, LHSV, SET) at each postbaseline time point at each dose level may be estimated using mixed model.

The relationship between the TTE endpoints and MYK-491 plasma concentration will be assessed using linear or nonlinear correlations.

11.3.7 *Safety Analyses*

All safety analyses except SET as determined by TTE will be performed on the Safety Analysis population. Analyses of SET as determined by TTE will be performed on the PD Analysis population.

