- ^f Triplicate 12-lead ECG evaluations taken within a 20-minute window will be performed in the supine position after 10 minutes of rest at Screening, Day -1, predose, and at 3, 5, 9, 12, 24, and 36 hours postdose. The predose ECG on Day 1 should be performed within 2 hours of dosing. The timing of the 12-lead ECGs in this table applies to patients enrolled in Cohort 1. The actual timing of the ECGs may be modified and/or up to an additional 2 ECGs may be requested by the SRC after review of the data from previous cohorts. The investigator may add extra 12-lead ECG safety assessments if there are any abnormal findings or if the investigator considers it required for any other safety reason. If the patient has any signs or symptoms suggestive of possible cardiac ischemia, additional ECGs should be obtained. These assessments should be recorded as unscheduled assessments.
- ^g Changes in a Baseline condition after the ICF is signed but before IMP is administered are recorded on the medical history eCRF unless the change is considered an AE related to a study procedure. All changes that occur after administration of the study medication are recorded as AEs.
- ^h A full TTE must be performed at Screening. After the Screening assessment, abbreviated TTEs will be performed predose, and at 3, 6, 9, and 24 hours postdose. It is important that the TTEs are completed as close as possible to the scheduled time. TTEs will be evaluated locally for changes that might affect dosing decision for others in the cohort, but the official reading will be done centrally by experts in a core laboratory in a blinded manner with results provided to the SRC. The SRC may modify the timing of the TTEs after the initial cohort so that for each subsequent cohort a TTE is obtained at the time of the predicted peak pharmacological effect. This will be based on the PK and TTE profiles from the previous cohorts. If appropriate, the SRC can request up to 2 additional TTEs be obtained.
- ⁱ [REDACTED]
- ^j ECG telemetry will be initiated at least 1 hour predose and continued through at least 48 hours. Additional monitoring may be needed based on data and/or patient's tolerance to the treatment.
- ^k Pregnancy tests, urine or blood based on the policy of the local institution or regulating Health Authority (eg, requirement for serum-based testing in the UK), should be performed on all females.

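### Part 1's placebo-adjusted PD change subtracts a single predose echo per period at full weight, and the optional mixed model names no predose covariate, so the crossover estimates may be less precise than the same data allow

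*Combined protocol and SAP*

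**What the plan says.** The Synopsis (Study Design) describes Part 1 thus: "This is a randomized, crossover, double-blind (DB), placebo-controlled, two-cohort, sequential ascending (oral) single-dose study in ambulatory patients with heart failure". Section 4.1.1 has treatment events "separated by no fewer than 5 days and no more than 14 days". The Synopsis (Sample Size Considerations) states "In Part 1, enrollment of 4-8 patients per cohort is planned".

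The Synopsis (Pharmacodynamic Analyses) ties Baseline to the period: "change from Baseline (predose in that dosing period) for each timepoint will be summarized by treatment arms". For the SAD cohorts it commits to the derived value: "placebo-adjusted change from Baseline will be calculated for each subject at each postbaseline timepoint and then summarized at each dose level". Section 11.3.6 repeats this commitment. Both places add that least-squares means of placebo-adjusted change may be estimated with a mixed model. Neither names a predose covariate.

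Section 4.1.1 says "A full PK profile and multiple TTEs and ECGs will be obtained at Baseline and after each dose", which could suggest several baseline echoes. The schedule does not have them. Footnote h of Table 3 in Appendix 1 reads "abbreviated TTEs will be performed predose, and at 3, 6, 9, and 24 hours postdose", which is one predose echo per period, and Table 4 (split dose) is the same.

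**The concern.** In a crossover each patient is their own control. Dose minus placebo at the same timepoint already removes the patient's own level. What the predose echo adds is information on that day's level, such as loading conditions. One echo measures that level with error, and subtracting it in full carries all of the error into the result, once for the active period and once for placebo. The best weight on the predose difference is rho, not 1.

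At stake is the precision of the placebo-adjusted effects on LVSV, LVEF, LVFS and SET, which are secondary objectives, in cohorts of 4 to 8 patients.

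**Working it through.** **Inputs.** From the documents: crossover, period-specific predose Baseline, one predose echo per period, 4 to 8 patients per cohort. The documents give no SD, correlation, effect size or power, so there is no planned figure to reproduce. rho is an assumption, shown over 0 to 0.8.

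**Model.** Echo reading = patient level + period (day) level + echo error. Within a patient, the variance of one echo is v = Vperiod + Vecho, and rho = Vperiod/v.

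**Variance per patient of each dose-minus-placebo value**

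- Planned double difference: the patient and period levels cancel and four echo errors remain, so 4·Vecho = 4v(1 − rho).
- Postdose difference without baseline: 2v.
- Postdose difference adjusted for the predose difference with slope rho: 2v(1 − rho²).

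Planned over adjusted is 4(1 − rho) / [2(1 − rho)(1 + rho)] = 2/(1 + rho). Planned over no-baseline is 2(1 − rho).

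| rho | planned / adjusted | planned / no baseline |
|---|---|---|
| 0 | 2.00 | 2.0 |
| 0.3 | 1.54 | 1.4 |
| 0.5 | 1.33 | 1.0 |
| 0.8 | 1.11 | 0.4 |

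The last column shows that above rho = 0.5 the planned value beats a difference that ignores Baseline.

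**Small samples, slope estimated.** Simulation with three periods per patient, patient and treatment effects, and the period's predose value as covariate. Variance ratio, planned over adjusted (repeat runs differ by up to about 0.1):

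| Setting | rho 0 | 0.3 | 0.5 | 0.8 |
|---|---|---|---|---|
| One cohort of 4 | 1.60 | 1.24 | 1.03 | 0.90 |
| One cohort of 8 | 1.89 | 1.41 | 1.21 | 1.02 |
| Two cohorts of 4, shared slope | 1.8 | 1.4 | 1.2 | 1.0 |
| Two cohorts of 8, shared slope | 1.9 | 1.5 | 1.3 | 1.1 |

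**Confidence intervals.** The fair comparator is a model of change from Baseline with the same patient and treatment effects and the same pooled residual variance, but no covariate. Excess width of its 95% CI over the covariate model:

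| Setting | rho 0 | 0.3 | 0.5 | 0.8 |
|---|---|---|---|---|
| One cohort of 4 | 23% | 8% | 0% | −8% |
| One cohort of 8 | 35% | 18% | 11% | 1% |
| Two cohorts of 4, shared slope | 35% | 18% | 9% | 0% |
| Two cohorts of 8, shared slope | 39% | 22% | 13% | 3% |

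**The case against.** **The planned table matches the stated endpoint.** Section 11.2.2 defines the endpoints as change from Baseline, Section 3.2 compares with Baseline and placebo, and Section 11.3.6 rules out inferential analysis. This stands. It is a reason to keep the table and to grade the point as precision only.

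**The mixed model is already foreseen.** It is optional and its covariates are unspecified, not excluded. Section 11.3 calls the text an outline and leaves full detail to a SAP, which is not in the text reviewed. This stands in part: the repair is to specify a model the plan already contemplates. In complete data, however, that model fitted to change without a predose covariate gives the same estimate as the double difference.

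**The predose echo removes real day-to-day variation.** Periods are 5 to 14 days apart, and the Synopsis and Section 7.6 both show concern about loading conditions. This stands. A reader might infer that the plan carries four echo errors where two would do, so Baseline should be dropped. The documents do not support that, because without Baseline the day's level remains, and above rho = 0.5 that costs more than it saves.

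**Larger CI penalties.** Comparing a paired t interval from the double differences (3 df with 4 patients) with the covariate model (5 df) makes the planned interval look 53% wider at rho = 0, and still 14% wider at rho = 0.8, where the planned value has the smaller variance (ratio 0.88). That comparison mixes in the gain from pooling residual variance, which a change-based model would also deliver, so it should not be used.

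**Dose selection.** A reader might infer that escalation decisions suffer. The documents do not show this. The escalation rule in Section 4.2.2 uses Baseline-corrected group means, with placebo adjustment only optional.

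**Extra echoes.** The SRC may add up to two TTEs per dosing period, but none need be predose. A second predose echo would reduce the planned variance from 4v(1 − rho) to 2(1 + 1/2)v(1 − rho) = 3v(1 − rho).

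**Conclusion.** The point holds as a loss of precision. Full subtraction of a single predose echo gives a placebo-adjusted value whose large-sample variance is 2/(1 + rho) times what covariate adjustment achieves: between 1.11 and 2.0 for rho from 0.8 to 0. The real excess is probably below the ceiling, since some day-to-day variation is to be expected, but the documents give no figure to place it. With a slope shared over two cohorts the ratio is about 1.4 to 1.5 at rho = 0.3 and 1.0 to 1.1 at rho = 0.8. A ratio of 1.4 is equivalent to giving up about 29% of the patients (1 − 1/1.4).

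This rests on the variance-component model, on the assumed rho, and on absolute change. Section 11.3.6 also allows percent change, for which the formula is only approximate. There is no bias and no error-rate problem, and the analysis is descriptive and secondary. It is worth correcting mainly because the correction is cheap.

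**What to change.** In Section 11.3.6 and the SAP, change the Part 1 mixed model from optional to committed. Specify patient and treatment effects and the period's predose value as a covariate, with one common slope across doses and cohorts. Either the postdose value or the change may be the response, because with the predose covariate in the model the treatment estimate is the same. Report dose minus placebo at each timepoint with a 95% CI. Keep the per-patient placebo-adjusted change table as the descriptive summary.

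The cost is SAP wording and one degree of freedom, since the echoes are already scheduled. If rho is near 0.8 there is little or no gain. If the slope is then fitted in a single cohort of 4, variance rises by about 10% (1/0.90 = 1.11), which is why the slope should be shared.
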